## 2 RESEARCH QUESTION AND OBJECTIVES

This non-interventional study was designed to investigate the effectiveness of OM-85 and to understand the management of patients with RTIs in routine clinical practice in Belgium, Italy, and China among adult and paediatric (aged  $\geq 1$  year) patients with recurrent RTIs ( $\geq 1$  RTI episodes within 12 months before CED). To investigate the effectiveness of OM-85 in patients with recurrent RTIs, RTI patients initiating OM-85 will be compared to RTI patients not initiating OM-85 (SOC/non-user group).

The objectives assessed in this study are described below. The populations included in each of the objectives are described in [Section 3.2.2](#), and outcomes assessed for the objectives in [Section 3.3.2](#). The objectives will be studied separately in each study country: Belgium, Italy, and China. Conducting summarised analysis combining the results of the countries for some of the objectives may be considered in the statistical analysis plan (SAP).

### 2.1 Primary Objectives

- **Primary objective 1: RTI rate 12 months before and 12 and 24 months after initiating OM-85:** To describe and compare the rate of RTIs episodes 12 months before initiating preventive treatment with OM-85 and 12 and 24 months after the initiation.
- **Primary objective 2: Comparative effectiveness – rate of RTI episodes during follow-up at 12 and 24 months:** To compare the rate of RTI episodes during the follow-up at 12 and 24 months, in patients initiating preventive treatment with OM-85 and in comparable patients not initiating OM-85 (SOC/non-user group).

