**Figure 1 Study Design**

Note: CED: cohort entry date; RTI: respiratory tract infection; SOC: standard of care

-  For the patients who initiate OM-85 during the initiation grace period, another index date is assigned at the date of the 1st OM-85 prescription: OM-85 initiation date. This date is used as the index date in analyses on exclusively OM-85 initiators.
-  Outcomes defined for each objective are listed in [Table 7](#) and [Table 8](#).
-  Pregnancy at CED is estimated using a variable assessment window expanding from 183 days (6 months) before CED to 280 days (9 months) after CED, as detailed in [Section 3.2.2.3](#).
-  Selected covariates are defined during initiation grace period, to be used in sensitivity analysis for clone censor weighting.

period (see [Section 3.3.3](#)).

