- **CED:** The CED is defined during the inclusion period, as the date of the 2nd, 3rd, ... or nth RTI episode during the inclusion period (see inclusion criteria in [Section 3.2.2](#)). This is also the date when a patient fulfils all the eligibility criteria. The CED can occur any time during the inclusion period. If a patient meets the eligibility criteria more than once during the inclusion period, and thereby has several candidate CEDs, the CED used in the study will be selected at random, which is one of the unbiased methods of selection of index date (29). The CED defines the end of the baseline period and the start of the initiation grace period for each included patient.

- **Baseline period:** The baseline period for each included patient is defined as the time before the CED. The minimum baseline period will be 12 months, and the maximum baseline period will be as long as data are available in each country (from January 2005 in Belgium, from January 1994, for GPs and 2017 for paediatricians, in Italy, and from January 2018 in China). The minimum baseline period of 12 months will be used for assessing the RTI rate during the baseline period and other baseline variables ([Section 3.7.4.1](#)). The maximum baseline period (all available data) will be used for selected variables, such as comorbidities (e.g., allergies, myocardial infarction, and cancer, see [Table 8](#)), since these could have occurred earlier but may not have been recorded in the data during the 12-month baseline period. Extending the 12-month baseline period for such variables is expected to improve the accurate classification of them (i.e., decreases the risk of covariate misclassification).
- **Initiation grace period:** For each included patient, a 30-day initiation grace period starting from the CED will be applied, to allow the included patients to initiate OM-85 during a reasonable period after the CED, as it is unrealistic to expect that OM-85 would in clinical practice be prescribed on the date of meeting the eligibility criteria ([28,29](#)).
- **OM-85 initiation date:** The OM-85 initiation date will be the date of the first observed prescription of OM-85 during the 30-day initiation grace period, starting from the CED. This is applicable only for the OM-85 exposure group.

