### 3.2.2 Study Population

The overall study population will include patients  $\geq 1$  year of age with  $\geq 1$  RTI episodes and no prescriptions of bacterial lysates within 12 months prior to inclusion to the study. Additionally, included patients will be required to have  $\geq 12$  months of continuous enrolment in the database prior to inclusion. The inclusion criteria are detailed in [Table 4, Section 3.2.2.1](#). No exclusion criteria are applied for this study.

The CED is the date of the 2nd, 3rd, ... or nth RTI episode, i.e., the date of fulfilling this inclusion criterion. During the inclusion period, patients can have several CEDs. For patients with several CEDs, the CED of the patient used in the study will be selected randomly, which is one of the unbiased methods to select the date (29). Thus, each patient can enter the study only once.

Patients in the overall study population will be categorised to one of the two exposure groups (treatment strategies): patients who initiated OM-85 at the CED or during the 30-day initiation grace period, and SOC/non-user group of patients who did not initiate OM-85 at the CED or during the 30-day initiation grace period.

The primary and secondary objectives and the exploratory objectives **CCI** will be studied in the overall study population ([Table 3](#)). The exploratory objectives **CCI** **CCI** **CCI**. The sub-populations applied in this study are further described in [Section 3.2.2.3](#).

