**Table 3 Populations for Each Study Objective**

Objective		Population In Which Studied and Index Date
Primary objectives		
1	RTI rate 12 months before and 12 and 24 months after initiating OM-85	
 
OM-85 initiators only, within the overall study population
 
Index date: OM-85 initiation date
 

2	Comparative effectiveness – rate of RTI episodes during follow-up at 12 and 24 months	
 
Both exposure groups (OM-85 initiators and SOC/non-user group) within the overall study population
 
Index date: end of initiation grace period
 

Secondary objectives		
1	Patient characteristics at CED	
 
Both exposure groups (OM-85 initiators and SOC/non-user group) within the overall study population
 
Index date: CED
 

2	Descriptive pattern of prescribing OM-85	
 
OM-85 initiators only, within overall study population
 
Index date: OM-85 initiation date
 

3	RTI rate 12 months before and 6 and 9 months after initiating OM-85	
 
OM-85 initiators only, within the overall study population
 

Objective		Population In Which Studied and Index Date
		
 
Index date: OM-85 initiation date
 

4	Comparative effectiveness – rate of RTI episodes during follow-up at 6 and 9 months	
 
Both exposure groups (OM-85 initiators and SOC/non-user group) within the overall study population
 
Index date: end of initiation grace period
 

5	Descriptive pattern of prescribing antibiotics during follow-up	
 
Both exposure groups (OM-85 initiators and SOC/non-user group) within the overall study population
 
Index date: end of initiation grace period
 

6	Descriptive pattern of concomitant medications of interest during follow-up	
 
Both exposure groups (OM-85 initiators and SOC/non-user group) within the overall study population
 
Index date: end of initiation grace period
 

7	Descriptive healthcare resource utilisation during follow-up	
 
Both exposure groups (OM-85 initiators and SOC/non-user group) within the overall study population
 
Index date: end of initiation grace period
 

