**Table 4 Inclusion Criteria**

	Inclusion Criteria	Operational Definition
1	Patient aged $\geq 1$ year of age at CED	Aged $\geq 1$ year at CED
2	Patient has $\geq 1$ RTI episodes during the 12-month baseline period prior to CED	$\geq 1$ RTI episodes within a 12-month period during the inclusion period. The CED is the date of the 2 nd , 3 rd , ... or n th RTI episode (i.e., date of fulfilling the inclusion criteria). If one patient has multiple CED during the inclusion period, the CED will be selected randomly. The definition of an RTI episode provided in Section 3.3.2.1
3	Patient has $\geq 12$ months of continuous enrolment in the database prior to CED	$\geq 12$ months of continuous enrolment in the database prior to the CED. Operationally, patients were required to have entered the database at least 12 months before the CED to be included in the study. In THIN (Belgium and Italy), this can be defined by a district variable for entry to the database: first contact date. In Inspur (China), patients are required to have records in the database at least 12 months before the CED (during the 12-month baseline period) to be eligible for inclusion
4	No record of a prescription of any bacterial lysates in the 12-month baseline period prior to CED	No record of the country-specific drug codes ( Appendix 4 ) during the 12-month baseline period

Note: CED: cohort entry date; RTI: respiratory tract infection; THIN: The Health Improvement Network.

Inclusion criterion 2 on the requirement of having  $\geq 1$  prior RTI episodes is important to apply because OM-85 is indicated for prevention of recurrent RTIs (24). However, patients in the SOC/non-user comparator group may still have fewer prior recurrent RTIs than the OM-85 group receiving preventive therapy. Therefore, prior recurrent RTIs will also be used in the PS matching of the compared exposure groups. The impact (preventive effect) of OM-85 on the recurrence of RTIs is anticipated to be higher in patients with an increased recurrence risk (35). Hence, the analyses will also be stratified by the number of RTI episodes prior to CED (see [Table 5](#)).

The inclusion of patients is not defined by sex. Sex is instead defined at CED and considered in the PS.

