### **3.7.3 Analysis of Primary Endpoint: RTI Rates (Primary Objectives 1-2, Secondary Objectives 3-4, Exploratory Objectives CCI)**

The primary outcome is the rate of RTIs episodes measured during different periods of interest, as specified in the objectives. The rate of RTI episodes will be estimated by calculating the total number of RTI episodes observed, divided by the total number of person-time (e.g., person-years) during a period of interest. Rates of RTI episodes will be estimated separately in patients initiating preventive treatment with OM-85 and in the SOC/non-user group. Furthermore, rates of RTI episodes during the baseline period will serve as reference in each treatment group to evaluate the effects of therapy during follow-up.

Comparative analysis comparing the RTI rates before and after OM-85 initiation, and analysis comparing RTI rates in the two exposure groups will be performed using approaches as described in the General Considerations. Generalised linear models with a Poisson distribution or negative binomial distribution (to account for over-dispersion) will be used to estimate the association between the initiation of OM-85 and the outcome of RTI rates, with the natural logarithm of the time at risk as offset (42).

The analyses will be identical for the exploratory objectives **CCI** **CCI** (Section 3.2.2.3).

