#### 3.9.1.1 Before-After Design Among OM-85 Initiators (Primary Objective 1, Secondary Objective 3, Exploratory Objectives CCI)

In the before-after design, differences in the rates of RTI episodes before and after initiation of OM-85 may be caused by factors other than the OM-85 initiation, factors that differ over the compared time periods. Such factors include progression of the patient's health condition (e.g., COPD), changes in the healthcare system or in access to care (opportunities to detect and record outcomes decrease if access to care decreases), and changes in infection rates in the studied population. Therefore, the results must be interpreted with caution.

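### Primary objective 1 compares a year selected for having RTIs with an unselected period afterwards, so an inert drug is expected to give a before/after IRR below 1

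*Protocol*

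**What the plan says.** Section 2.1 sets primary objective 1 as a comparison of RTI rates: "compare the rate of RTIs episodes 12 months before initiating preventive treatment with OM-85 and 12 and 24 months after the initiation". Table 3 restricts it to OM-85 initiators and gives "Index date: OM-85 initiation date". Note 1 to Figure 1 says of the initiation date: "This date is used as the index date in analyses on exclusively OM-85 initiators".

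Eligibility is built on the outcome. Table 4 asks for one or more "RTI episodes during the 12-month baseline period prior to CED". Section 3.2.2 defines the CED as the date of the second or a later "RTI episode, i.e., the date of fulfilling this inclusion criterion". Section 3.3.1.2 places OM-85 initiation at the CED or within the 30-day grace period after it.

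Section 3.2.1 ends the baseline period at the CED, not at initiation, and states: "The minimum baseline period of 12 months will be used for assessing the RTI rate during the baseline period". Section 3.7.3 adds that "rates of RTI episodes during the baseline period will serve as reference in each treatment group to evaluate the effects of therapy during follow-up".

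Section 3.7.1 fits a generalised linear model with a before/after flag as the independent variable and reports an estimate, 95% CI and p-value. Section 3.9.1.1 warns that other factors may explain a before/after difference: "Such factors include progression of the patient's health condition (e.g., COPD), changes in the healthcare system or in access to care", together with changing infection rates.

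**The concern.** Patients enter because they have just had an RTI and had another in the preceding year. Counting RTIs in that year and comparing them with a period that carries no such requirement produces a fall even if the drug does nothing. This is regression to the mean caused by selecting on the outcome.

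A before/after IRR tested against 1 is then tested against the wrong neutral value. Section 3.1 names the before-after design as one of the two ways in which effectiveness is assessed, and it is the only objective with a study-size calculation. An artefact as large as the planned effect could be reported as benefit.

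The size depends on whether the CED episode falls in the window, and there the protocol disagrees with itself. Counting back from initiation normally includes it when the prescription follows the CED day. Counting back from the CED leaves it out.

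**Working it through.** **Inputs.** Rate 2 per person-year, equal person-time, IRR 0.9, 350 person-years (PY) per group and a CI width of at most 0.2 (section 3.5 and Table 9). At least one RTI in the 12 months before the CED (Table 4). CED is an RTI date (section 3.2.2). Lag to initiation 0 to 30 days (section 3.3.1.2). Maximum episode length 14 days (section 3.3.2.1).

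**The plan's own figure.** Using the F-based CI in section 3.5 with b = 2 × 350 = 700 and a = 0.9 × 700 = 630, the interval is 0.807 to 1.004, width 0.197. This matches Table 9 (300 PY gives 0.213, also as stated). All 32 cells of the table reproduce, so the precision arithmetic is not at fault.

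**Expected IRR for an inert drug.** Assume a constant Poisson rate L per year, unchanged by treatment.

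- After, per year: L.
- Before, window ending at the CED: the mean given at least one event, L / (1 − e^(−L)). The null IRR is therefore 1 − e^(−L).
- Before, window ending at initiation with the CED episode inside it: L / (1 − e^(−L)) + 1. The null IRR is L divided by that.

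At L = 2, 2 / (1 − 0.1353) = 2.313. The null IRR is 2 / 2.313 = 0.865 without the CED episode and 2 / 3.313 = 0.604 with it.

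| Assumed rate per year | Null IRR, CED episode counted | Null IRR, window ends at CED |
|---|---|---|
| 1 | 0.39 | 0.63 |
| 2 (plan) | 0.60 | 0.86 |
| 3 | 0.72 | 0.95 |
| 4 | 0.79 | 0.98 |

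**At the planned size.** With 350 PY each side, the expected counts after and before are 700 and about 1,160 (CED episode counted), or 700 and about 810 (not counted). The section 3.5 formula gives 95% CIs of 0.549–0.664 and 0.780–0.958. Both exclude 1 with no drug effect. That formula treats the two periods as independent, whereas the analysis will use cluster-robust standard errors, so these intervals only illustrate scale.

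**Simulation check at 2 per year, no drug effect.** One CED was drawn at random per patient, with a 0–30 day lag and 14-day episodes, inclusion periods of 3.5 and 16.5 years, and both fixed and gamma-varying patient rates. The 12-month IRR was about 0.55–0.62 with the CED episode and about 0.82–0.87 without it. The 24-month annualised IRR with the CED episode was 0.57–0.63. If every prescription fell on the CED day and the index day were not counted, the values were 0.79 at 12 months and 0.84 at 24 months.

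**The case against.** The best defence is that the before-after design is framed in section 3.1.1 as reference data, that section 3.9.1.1 lists its factors as examples and asks for caution, that section 3.7.3 plans baseline rates in both groups, and that primary objective 2 is the controlled contrast, with prior RTIs in the propensity score. All of that is in the text. None of it changes the objective 1 estimate, which section 3.1 presents as an assessment of effectiveness and section 3.7.1 reports with a p-value. A general caution also differs from naming a bias whose expected direction under these definitions is known.

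A reader might infer that the window must contain the CED episode, so that 0.60 is the established figure. The documents do not support that. Section 3.2.1 points to a window ending at the CED, same-day prescriptions depend on how the index day is counted, and a qualifying RTI late in the look-back can drop out when the window moves forward (about 2% of patients had fewer than two episodes before initiation in the simulation at 2 per year). Figure 1 is not shown, and Table 7 and section 3.7.8 are redacted, so the window may be settled there.

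A reader might also infer that a significant reduction is bound to appear whatever OM-85 does, or that the net bias must favour it. That does not follow either. With the CED episode excluded, the null IRR is 0.95 at 3 per year and 0.98 at 4 per year, and section 3.9.2.2 describes a detection bias acting the other way.

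**Conclusion.** The point stands. The period before is selected on RTIs and the period after is not, so the expected IRR under no effect is below 1. At the plan's own 2 per person-year the artefact is about 40% with the CED episode and about 14% without it, against the 10% effect used for study size. It is material at 2 per year or below on either reading, and small at high rates only if the CED episode is excluded.

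The figures rest on a constant underlying rate and on the planning value, which is a population rate and not one observed in this cohort. Preferential prescribing after a bad year, which the protocol does not quantify, could enlarge the artefact. The gap in the limitations is claimed only for the visible text of section 3.9.1.1. Secondary objective 3 uses the same comparison and has the same weakness.

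**What to change.** 1. Reconcile sections 2.1 and 3.2.1, Table 3 and the Figure 1 note on one window for the period before. It should end the day before the CED for every patient and never count the CED episode.
2. That step alone leaves a null IRR of about 0.86 at 2 per year. Base any effectiveness inference on the before/after change in initiators relative to the same change in PS-matched SOC patients, on a common time anchor, using a period-by-group term with clustering by patient. Present the single-arm IRR as descriptive and non-causal.
3. Where at least 24 months of history exist, add a supportive comparison with months 13–24 before the CED. The simulated null IRR there is about 0.93–1.00 at 2 per year. It will be missing for early Chinese entrants (data from January 2018, inclusion from January 2019) and for the youngest children.
4. Name regression to the mean through selection on prior RTIs in section 3.9.1.1.
5. Apply the same changes to secondary objective 3.

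The cost is wording and one model term, since baseline rates in both groups are already planned. The headline before/after figure will look less favourable, and the controlled contrast will lie close to primary objective 2 because matching uses prior RTIs.

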### 2.2 Secondary Objectives

- **Secondary objective 1: Patient characteristics at CED:** To describe the baseline characteristics of patients initiating preventive treatment with OM-85 and patients not initiating OM-85 (SOC/non-user group) with respect to demographics, type of previous RTI episodes (URTI, LRTI, Other RTIs), comedications, antibiotic use, comorbidities and number of healthcare visits.

- **Secondary objective 2: Descriptive pattern of prescribing OM-85:** To describe the pattern of prescribing OM-85 (e.g., dose, duration, number of cycles) among patients initiating preventive treatment with OM-85, at OM-85 initiation date and in follow-up at 3, 6, 9, 12 and 24 months after initiating OM-85.
- **Secondary objective 3: RTI rate 12 months before and 3, 6 and 9 months after initiating OM-85:** To describe and compare the rate of RTIs episodes 12 months before initiating preventive treatment OM-85 and 3, 6, and 9 months after the initiation.
- **Secondary objective 4: Comparative effectiveness – rate of RTI episodes during follow-up at 6 and 9 months:** To compare the rate of RTI episodes during the follow-up at 3, 6, and 9 months in patients initiating preventive treatment with OM-85 and in the patients not initiating OM-85 (SOC/non-user group).
- **Secondary objective 5: Descriptive pattern of prescribing antibiotics during follow-up:** To describe the pattern of prescribing specific antibiotics during follow-up at 3, 6, 9, 12, and 24 months, in patients initiating preventive treatment with OM-85 and in patients not initiating OM-85 (SOC/non-user group).
- **Secondary objective 6: Descriptive pattern of concomitant medications of interest during follow-up:** To describe the pattern of specific concomitant medications of interest during follow-up at 3, 6, 9, 12, and 24 months, in patients initiating preventive treatment with OM-85 and in patients not initiating OM-85 (SOC/non-user group).
- **Secondary objective 7: Descriptive healthcare resource utilisation during follow-up:** To describe overall and RTI episode-specific healthcare visits (general practitioner, specialist care visit, hospital admissions, and emergency department visits) at 3, 6, 9, 12, and 24 months in patients initiating preventive treatment with OM-85 and in patients not initiating OM-85 (SOC/non-user group).

### 2.3 Exploratory Objectives

CCI [REDACTED]

CCI [REDACTED]

CCI [REDACTED]

CCI [REDACTED]

CCI [REDACTED]

CCI [REDACTED]

CCI [REDACTED]

CCI [redacted]  
CCI [redacted]  
CCI [redacted]  
CCI [redacted]  
CCI [redacted]  
CCI [redacted]

CCI [redacted]  
CCI [redacted]  
CCI [redacted]  
CCI [redacted]  
CCI [redacted]

CCI [redacted]  
CCI [redacted]  
CCI [redacted]

CCI [redacted]  
CCI [redacted]  
CCI [redacted]  
CCI [redacted]  
CCI [redacted]

CCI [redacted]  
CCI [redacted]  
CCI [redacted]  
CCI [redacted]  
CCI [redacted]

CCI [redacted]  
CCI [redacted]

CCI [redacted]  
CCI [redacted]  
CCI [redacted]  
CCI [redacted]

CCI [redacted]  
CCI [redacted]  
CCI [redacted]  
CCI [redacted]

CCI [Redacted]  
CCI [Redacted]  
CCI [Redacted]  
CCI [Redacted]

CCI [Redacted]  
CCI [Redacted]  
CCI [Redacted]  
CCI [Redacted]

CCI [Redacted]  
CCI [Redacted]  
CCI [Redacted]  
CCI [Redacted]

CCI [Redacted]  
CCI [Redacted]  
CCI [Redacted]  
CCI [Redacted]

